8.1.1. Liver Chemistry Stopping Criteria

Liver chemistry stopping and increased monitoring criteria have been designed to assure participant safety and evaluate liver event etiology (in alignment with the FDA premarketing clinical liver safety guidance). These protocol guidelines are in alignment with FDA premarketing clinical liver safety guidance:

<http://www.fda.gov/downloads/Drugs/GuidanceComplianceRegulatoryInformation/Guidances/UCM174090.pdf>.

Discontinuation of study treatment for abnormal liver tests should be considered by the investigator when a participant meets one of the conditions outlined in the algorithm or if the investigator believes that it is in the best interest of the participant.

Phase II Liver Chemistry Stopping and Increased Monitoring Algorithm

Liver Safety Required Actions and Follow up Assessments can be found in [Appendix 7](#)

8.1.2. QTc Stopping Criteria

Details on performing ECG assessments can be found in Section [9.4.3](#).

The *same* QT correction formula *must* be used for *each individual participant* to determine eligibility for and discontinuation from the study. This formula may not be changed or substituted once the participant has been enrolled.

- For example, if a participant is eligible for the protocol based on QTcB (QT interval corrected for heart rate by Bazett's formula), then QTcB must be used for discontinuation of this individual participant as well.
- Once the QT correction formula has been chosen for a participant's eligibility, the *same formula* must continue to be used for that participant *for all QTc data being collected for data analysis*. Safety ECGs and other non-protocol specified ECGs are an exception.

The QTc should be based on averaged QTc values of triplicate electrocardiograms obtained over a brief (e.g., 5-10 minute) recording period.

For this study, the following QTc stopping criteria will apply, lead to withdrawal from study treatment:

- QTc>500 msec or uncorrected QT>600 msec
- Change from baseline: QTc> 60 msec
- For patients with underlying bundle branch block, follow the discontinuation criteria listed below:
 - Baseline QTc with Bundle Branch Block <450 msec, Discontinuation QTc with Bundle Branch Block >500 msec
 - Baseline QTc with Bundle Branch Block <450-480 msec, Discontinuation QTc with Bundle Branch Block \geq 530 msec

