8. **Clinically significant ECG abnormality:** Evidence of a clinically significant abnormality in the 12-lead ECG performed during screening or run-in. The PI will determine the clinical significance of each abnormal ECG finding in relation to the participant's medical history and exclude participants who would be at undue risk by participating in the trial. An abnormal and clinically significant finding is defined as a 12-lead tracing that is interpreted as, but not limited to, any of the following:

- AF with rapid ventricular rate >120 beats per minute (BPM)
- sustained or nonsustained ventricular tachycardia (VT)
- Second degree heart block Mobitz type II and third degree heart block (unless pacemaker or defibrillator had been inserted)
- QTcF \geq 500 msec in patients with QRS <120 msec and QTcF \geq 530 msec in patients with QRS \geq 120 msec

9. **Unstable or life threatening cardiac disease:** participants with any of the following at Screening (Visit 1) would be excluded:

- Myocardial infarction or unstable angina in the last 6 months
- Unstable or life threatening cardiac arrhythmia requiring intervention in the last 3 months
- New York Heart Association (NYHA) Class IV Heart failure

10. **Antimuscarinic effects:** Participants with a medical condition such as narrow-angle glaucoma, urinary retention, prostatic hypertrophy or bladder neck obstruction should only be included if in the opinion of the Investigator the benefit outweighs the risk and that the condition would not contraindicate study participation.

11. **Cancer:** Participants with carcinoma that has not been in complete remission for at least 5 years. Participants who have had carcinoma *in situ* of the cervix, squamous cell carcinoma and basal cell carcinoma of the skin would not be excluded based on the 5 year waiting period if the participant has been considered cured by treatment.

12. **Questionable validity of consent:** Participants with a history of psychiatric disease, intellectual deficiency, poor motivation or other conditions that will limit the validity of informed consent to participate in the study.

PRIOR/CONCOMITANT THERAPY

13. **Medication prior to spirometry:** Participants who are medically unable to withhold their albuterol/salbutamol for the 6-hour period required prior to spirometry testing at each study visit.

PRIOR/CONCURRENT CLINICAL STUDY EXPERIENCE/RELEVANT HABITS

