8. DISCONTINUATION CRITERIA

8.1. Discontinuation of Study Treatment

Participants that permanently stop study treatment are encouraged to remain in the study. Participants have the right to discontinue study treatment before the end of the study. A participant may also be asked to discontinue study treatment at the Investigator's discretion.

Participants who withdraw from study treatment prematurely (for any reason) should, where possible, continue to be followed-up as per protocol until the completion of the Safety Follow-up assessments. If this is not possible, the Investigator must encourage the participant to participate in as much of the study as they are willing (or able) to.

A participant may be withdrawn from study treatment at any time. A reason for premature discontinuation of study treatment (e.g., AE, lack of efficacy [including moderate or severe asthma exacerbation], protocol deviation, Investigator discretion, consent withdrawn etc.) must be captured in the eCRF.

A participant must be withdrawn from study treatment if any of the following stopping criteria are met:

- Liver Chemistry: Meets any of the protocol-defined liver chemistry stopping criteria
- QTc: Meets any of the protocol-defined stopping criteria
- Pregnancy: Positive pregnancy test

[figure not shown]

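### For QRS of 120 msec or more, the QTc stopping limits in Section 8.1.2 do not fit the entry limit in exclusion 8

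*Protocol*

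**What the plan says.** **Entry (Protocol, Section 6.2, exclusion 8).** The limit depends on QRS width. The criterion excludes QTcF at or above "500 msec in patients with QRS <120 msec and QTcF" at or above "530 msec in patients with QRS" at or above 120 msec. The list of findings is open-ended, and the investigator may exclude others at undue risk. High-grade heart block is not counted as an excluding finding when a device is in place: "third degree heart block (unless pacemaker or defibrillator had been inserted".

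**Stop (Protocol, Section 8.1.2).** Two general limits carry no QRS condition: "QTc>500 msec or uncorrected QT>600 msec" and "Change from baseline: QTc> 60 msec". A third bullet says: "For patients with underlying bundle branch block, follow the discontinuation criteria listed below". Two rows follow. The first takes a baseline below 450 msec and stops above 500 msec. The second reads "Baseline QTc with Bundle Branch Block <450-480 msec, Discontinuation QTc with Bundle Branch Block" at or above 530 msec. No row goes beyond a baseline of 480 msec. The stop is judged on the average of triplicate ECGs, using the same correction formula as for eligibility.

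**Force of the stop (Protocol, Section 8.1).** "A participant must be withdrawn from study treatment if any of the following stopping criteria are met"; the QTc criteria are on that list.

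**Timing (Protocol, Section 2).** ECGs are scheduled at Visit 1, Visit 3 (Day 29), Visit 5 and early withdrawal. Visit 1 is the only scheduled ECG before treatment.

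**The concern.** An entry limit and a stopping limit on the same measurement should leave every eligible participant on the permitted side of the stop at baseline. Here the entry limit was widened for QRS of 120 msec or more, but the stop was widened only for bundle branch block, which is a different category, and only for baselines up to 480 msec.

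Two consequences follow. A stable wide-QRS participant without bundle branch block can be enrolled, dosed for four weeks and then withdrawn from treatment at Visit 3 for a value already present at screening. For a participant with bundle branch block and a baseline above 480 msec, the site cannot tell from the text which limit applies. Both concern individual safety decisions under a mandatory rule, and different sites could apply that rule differently.

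**Working it through.** All values are whole msec. Entry and stop are compared in the same QTc formula, as Section 8.1.2 requires. The protocol states no figure of its own to reproduce on this point.

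**Inputs**

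| Item | Source | Value |
|---|---|---|
| Highest entry value, QRS <120 | Exclusion 8 | 499 |
| Highest entry value, QRS ≥120 | Exclusion 8 | 529 |
| First value meeting the general absolute stop | Section 8.1.2 | 501 |
| Highest baseline with a bundle branch block row | Section 8.1.2 | 480 |
| First value meeting the second row's stop | Section 8.1.2 | 530 |
| First value meeting the change limit | Section 8.1.2 | baseline + 61 |

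**Step 1. QRS below 120 msec.** Entry ends at 499 and the stop begins at 501. Baselines that already meet the stop: 0. Entry and stop agree.

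**Step 2. QRS of 120 msec or more, no bundle branch block.** Entry ends at 529 and the stop begins at 501. Baselines that already meet the stop: 529 − 501 + 1 = 29 (501–529).

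**Step 3. Bundle branch block, QRS of 120 msec or more.** Baselines with no row: 529 − 480 = 49 (481–529). The text allows two readings.

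- *The general limits apply outside the rows.* Baselines 481–500 (20 values) stop at 501. Baselines 501–529 (29 values) already meet the stop, as in step 2. The rule also steps backwards: a baseline of 480 stops at 530, but a baseline of 481 stops at 501.
- *The general limits do not apply to bundle branch block.* No absolute QTc ceiling is stated for any of the 49 values.

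**Step 4. The second row's label.** Written as below 450 to 480, it overlaps the first row for every baseline under 450. Starting it at 450 removes the overlap.

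**Step 5. After the change proposed under fix.** The first stopping value is the smaller of the row limit and baseline + 61.

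| Group | Baseline | First stopping value |
|---|---|---|
| Bundle branch block | 449 | min(501, 510) = 501 |
| Bundle branch block | 450 | min(530, 511) = 511 |
| Bundle branch block | 468 | min(530, 529) = 529 |
| Bundle branch block | 469 to 529 | 530 |
| Wide QRS, no block | up to 500 | min(501, baseline + 61), unchanged |
| Wide QRS, no block | 501 to 529 | 530, or not eligible |

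Baselines that already meet a stop at entry: 0 in every group.

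**The case against.** **The stop errs towards caution.** Where entry and stop clearly conflict, the result is that drug is stopped, and Section 8.1 encourages the participant to stay in the study. Section 3.3.1 reports no QTcF difference from placebo at UMEC 500 mcg, eight times the highest dose here (500 / 62.5 = 8). This stands, and it limits the severity. It does not make the two limits agree.

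**Judgement and repeat ECGs may prevent it.** The investigator may exclude someone with a screening QTcF of 501–529. Entry rests on a single ECG (Section 9.4.3) and the stop on a triplicate average, so a value of 501–529 at entry need not recur. Both points are fair and reduce the number affected. Neither changes a threshold.

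**Three stronger readings are tempting and are not supported.**

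- A reader might infer that bundle branch block baselines of 481–529 have no ceiling and may run to 541–589 msec (baseline + 60). That holds only if the general absolute limits do not apply to participants outside the rows. Section 8.1.2 does not say so, and Section 8.1 acts on any criterion met. An equally coherent reading is that a row displaces the 500 msec limit only for those who match it. The defect is that the text does not choose.
- A reader might infer that a bundle branch block baseline below 450 is told both to stop and to continue. The second label is most likely a slip for 450–480, since it directly follows a row for baselines below 450. It needs correcting but is not a separate conflict of substance.
- A reader might infer that exclusion 8 expressly admits paced participants with wide QRS. The device wording only takes paced heart block off a list of abnormal findings; it says nothing about QRS width or QTc.

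**A broad repair would overshoot.** Applying the 530 msec stop to every wide-QRS participant with a baseline of 450 or more would loosen the stop for those without bundle branch block at 450–500, where entry and stop do not conflict today. This is right, and the fix is limited accordingly.

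**Conclusion.** The mismatch holds as written. For QRS of 120 msec or more without bundle branch block, 29 baseline values (501–529) pass the entry limit and already meet a mandatory stop. For bundle branch block, 49 baseline values (481–529) match no row. If the general limits apply to them, 501–529 has the same conflict; if not, no absolute QTc ceiling is stated. The second row should start at 450.

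This rests on three assumptions: whole-msec values, one correction formula for entry and stop, and QRS of 120 msec or more for the bundle branch block range (with QRS below 120 msec, entry ends at 499 and the unmatched range is 481–499).

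Severity is low. The protocol gives no frequency of wide QRS, so the number affected cannot be stated; it is probably small. Power, the primary analysis and the FEV1 result are essentially untouched.

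**What to change.** **Bundle branch block.** Replace the third bullet of Section 8.1.2 with: *For participants with bundle branch block, these rows replace only the QTc >500 msec limit: baseline <450 msec, stop at >500 msec; baseline 450–529 msec, stop at ≥530 msec. Uncorrected QT >600 msec and a change from baseline of >60 msec apply to all participants.*

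**QRS of 120 msec or more without bundle branch block.** Keep the >500 msec stop for baselines up to 500 msec. Remove the conflict at 501–529 only, in one of two ways:

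- a stop at ≥530 msec for those baselines; or
- more conservatively, exclusion of QTcF above 500 msec at entry for this group.

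**Cost.** A few sentences and no extra ECGs. Under the first option a very small number of participants continue at 501–529 msec, and the rule has a step: a baseline of 500 stops at 501, a baseline of 501 at 530. Under the second a very small number are excluded at screening, exclusion 8 must be amended, and there is no step. In bundle branch block, or under the first option, a baseline of 529 has a margin of 1 msec before the 530 stop, similar to the 2 msec of a narrow-QRS entrant at 499.

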8.1.3. Rechallenge

8.1.3.1. Study Treatment Restart or Rechallenge

Study treatment restart or rechallenge after liver chemistry stopping criteria are met by any participant in this study is not allowed.

8.2. Withdrawal from the Study

- A participant may withdraw from the study at any time at his/her own request, or may be withdrawn at any time at the discretion of the investigator for safety, behavioral, compliance or administrative reasons.
- If the participant withdraws consent for disclosure of future information, the sponsor may retain and continue to use any data collected before such a withdrawal of consent.
- If a participant withdraws from the study, he/she may request destruction of any samples taken and not tested, and the investigator must document this in the site study records.
- In the event of early withdrawal from the study, every effort should be made to have the participant to return to the clinic for an Early Withdrawal Visit and Safety Follow-up, and to return all study related materials. Assessments to be performed during the Early Withdrawal Visit and the Safety Follow-up contact are described in the Schedule of Activities table (Section 2).

8.3. Lost to Follow Up

A participant will be considered lost to follow-up if he or she repeatedly fails to return for scheduled visits and is unable to be contacted by the study site.

The following actions must be taken if a participant fails to return to the clinic for a required study visit:

- The site must attempt to contact the participant and reschedule the missed visit as soon as possible and counsel the participant on the importance of maintaining the assigned visit schedule and ascertain whether or not the participant wishes to and/or should continue in the study.
- Before a participant is deemed lost to follow up, the investigator or designee must make every effort to regain contact with the participant (where possible, 3 telephone calls and, if necessary, a certified letter to the participant's last known mailing address or local equivalent methods). These contact attempts should be documented in the participant's medical record.
- Should the participant continue to be unreachable, he/she will be considered to have withdrawn from the study with a primary reason of lost to follow-up.

9. STUDY ASSESSMENTS AND PROCEDURES

Study procedures and their timing are summarized in the Schedule of Activities (SoA) (Section 2). There are no protocol waivers or exemptions allowed. Immediate safety concerns should be discussed with the sponsor immediately upon occurrence or awareness to determine if the participant should continue or discontinue study treatment. Adherence to the study design requirements, including those specified in the SoA, is essential and required for study conduct.

No study related procedures may be performed until the informed consent form has been signed by the participant. A Pre-Screening visit (Visit 0) is required in order to administer the informed consent before any changes are made to the participant's current medical regimen. Selection and modification of the participant's medications prior to study participation is based on the physician's judgment according to sound medical practice, principles, and each participant's needs. A participant's treatment must not be changed merely for the purpose of enabling the participant's participation in the study.

During the Pre-Screening visit (Visit 0) the following information will be captured in the eCRF for each participant:

- Demographic information including race, age and gender
- Participant number
- Serious Adverse Event information only for any SAE considered as related to study participation
- Investigator signature page

The additional following critical baseline assessments will be conducted at Screening (Visit 1):

- Weight and height
- Asthma diagnosis history including:
 - The age of the participant when they were first provided with an inhaler for asthma
 - Completion of an asthma medical history questionnaire: a copy of this questionnaire and instructions for its use can be found in the SRM
- Smoking history and status
- Exacerbation history
- Asthma and other concurrent medications
- Medical History including previous and/or concurrent medical conditions, detailed cardiovascular risk factor history, pneumonia, and pneumonia vaccine status
- Reason for screen failure (if applicable)
- Vital signs
- Questionnaires (ACQ; E-RS)
- Pre-and post-albuterol/salbutamol lung function
- Inclusion/Exclusion criteria assessment
- Physical examination
- 12-lead ECG
- Child bearing status assessment for all potential female participants
- Clinical laboratory tests (including hematology, chemistry, urinalysis and serum pregnancy test)
- AE / SAE assessment

In addition, the following procedures must be completed at Screening (Visit 1):

- Electronic device training / dispense eDiary
- Review/dispense Medical Problems/Medication Taken worksheet
- Dispense FF 100 mcg run-in medication

9.1. Efficacy Assessments

The timings of all efficacy assessments are specified in the Schedule of Activities (SoA) (Section 2).

9.1.1. Questionnaires

The questionnaires should be completed before any procedures are performed on the participant to avoid influencing the participant's response. To avoid biasing responses, the participants should not be told the results of diagnostic tests prior to completing the questionnaires and it is recommended that the questionnaires be administered at the same time of day during each visit (as applicable) using the provided electronic device (unless otherwise specified). Adequate time must be allowed to complete all items on the questionnaires; the questionnaires must be reviewed for completeness and, if necessary, the participant must be encouraged to complete any missing assessments or items.

Instructions for completing the questionnaires can be found in the SRM.

9.1.1.1. Global Assessment of Severity and Response to Treatment

The participant will be asked to complete the Global Assessment of Severity and Response to Treatment at the visits specified in the Schedule of Activities table (Section 2). The Global Assessment of Severity is a single item questionnaire; participants are asked to rate their asthma symptoms at the study visit using a five-point scale (none, mild, moderate, severe, very severe). The Response to Treatment is a single question of the patient's overall evaluation of response to treatment, using a seven-point rating scale with the following definitions: 1 = significantly improved; 2 = moderately improved; 3 = mildly improved; 4 = no change; 5 = mildly worse; 6 = moderately worse; and 7 = significantly worse. Instructions for completing the questionnaires can be found in the SRM.

9.1.1.2. Asthma Control Questionnaire (ACQ)

The ACQ measures attributes of asthma control [Juniper 1999], measured with questions designed to be self-completed by the participant. Participants will complete the ACQ at specified study visits. The ACQ-5 includes five questions (concerning nocturnal awakening, waking in the morning, activity limitation, shortness of breath and wheeze) which enquire about the frequency and/or severity of symptoms over the previous week. The ACQ-6 includes an additional item asking about rescue medication use. The response options for all these questions consist of a zero (no impairment/limitation) to six (total impairment/ limitation) scale. The recall period is the past week. A score of <0.75 indicates well-controlled asthma and a score ≥ 1.5 indicates poorly controlled asthma [Juniper 2006]. A change of ≥ 0.5 in score suggests a clinically important change in score [Juniper 2005].

9.1.1.3. St. George's Respiratory of Life Questionnaire (SGRQ)

The SGRQ is a well established instrument, comprising 50 questions designed to measure Quality of Life in patients with diseases of airway obstruction, measuring symptoms, impact, and activity. The questions are designed to be self-completed by the participant [Jones 1992] with a recall over the past 3 months. A change of 4 points is considered a clinically relevant change [Jones 2005].

9.1.1.4. Asthma Quality of Life Questionnaire (AQLQ)

The AQLQ was developed to measure the functional impairments related to asthma experienced by adults 17+ years old. The AQLQ (+12), is a modified version of the original AQLQ and validated for use in asthma patients between the ages of 12 and 70 [Juniper 2005]. The response scale ranges from 1 (totally impaired) to 7 (not at all impaired). The questions are designed to be self-completed by the participant with a recall over the past 2 weeks. A change of ≥ 0.5 is considered clinically important [Juniper 1994].

9.1.2. Daily Diaries

Participants will be issued with a combination spirometer and eDiary device at Visit 1 for twice daily use (in the morning upon waking and in the evening just before going to bed) throughout the study. The eDiary device will be provided by a third-party vendor. Information on the device and its use are documented in the SRM and the third-party vendor manual. Participants will be instructed on how to use the device in order to record results for the following in the eDiary each day from Visit 1 onwards:

- Daily symptom assessment (E-RS and supplemental asthma items; night-time awakening, asthma symptom and physical activity questions)
- The number of inhalations of rescue albuterol/salbutamol used during the day and night.
- Morning and evening FEV1
- Morning and Evening PEF
- Morning FF 100 mcg medication use
- Morning double-blind study medication use (during the treatment period only)

Section 9.1.2 describes the assessments and questionnaires recorded on the eDiary device, as well as the alerts that can be triggered based on recorded results. The data from the eDiary device will be automatically transmitted to a centralised server.

Participants will also be issued with a paper Medical Problems/Medications Taken worksheet to record medical problems experienced and medications used during the study (please refer to the SRM for further details). Participants must also use this paper worksheet to record all healthcare contacts that occur during their participation in the study. This paper worksheet will be used to assist participant recall in discussions with the Investigator, for site staff to then enter as appropriate in the eCRF.

9.1.2.1. eDiary Questionnaires, Assessments and Alerts

For information on the eDiary questions, please refer to [Appendix 8](#).

